### 14.3.2 Listing of Deaths, Other Serious and Significant Adverse Events

**Table 104: Listing of Serious Adverse Events**

Adverse Event	Associated with Dose No.	No. of Days Post Associated Dose (Duration)	No. of Days Post Dose the Event Became Serious	Reason Reported as an SAE	Severity	Relationship to Study Product	If Not Related, Alternative Etiology	Action Taken with Study Treatment	Subject Discontinued Due to AE	Outcome	MedDRA System Organ Class	MedDRA Preferred Term
Vaccination Group: , Subject ID: , AE Number:												
Comments:												
Vaccination Group: , Subject ID: , AE Number:												
Comments:												

**Table 105: Listing of Non-Serious, Unsolicited, Moderate or Severe Adverse Events**

Adverse Event	Associated with Dose No.	No. of Days Post Associated Dose (Duration)	Severity	Relationship to Study Product	If Not Related, Alternative Etiology	Action Taken with Study Treatment	Subject Discontinued Due to AE	Outcome	MedDRA System Organ Class	MedDRA Preferred Term
Vaccination Group: , Subject ID: , AE Number:										
Comments:										
Vaccination Group: , Subject ID: , AE Number:										
Comments:										

---

#### **14.3.3 Narratives of Deaths, Other Serious and Significant Adverse Events**

(not included in SAP, but this is a placeholder for the CSR)

**14.3.4 Abnormal Laboratory Value Listings (by Subject)****Table 106: Listing of Abnormal Laboratory Results - Chemistry**

Vaccination Group	Subject ID	Sex	Age (years)	Planned Time Point	Actual Study Day	Number of Doses Received	Laboratory Parameter (Units)	Result (Severity)	Relationship to Treatment	If Not Related, Alternate Etiology	Action Taken with Study Treatment	Subject Discontinued Due to Result?

**Table 107: Listing of Abnormal Laboratory Results - Hematology**

Vaccination Group	Subject ID	Sex	Age (years)	Planned Time Point	Actual Study Day	Number of Doses Received	Laboratory Parameter (Units)	Result (Severity)	Relationship to Treatment	If Not Related, Alternate Etiology	Action Taken with Study Treatment	Subject Discontinued Due to Result?

### 14.3.5 Displays of Laboratory Results

#### 14.3.5.1 Chemistry Results

**Table 108: Abnormal Laboratory Results by Maximum Severity, Time Point, and Vaccination Group – Any Chemistry Parameter**

Time Point	Vaccination Group	ANDV DNA Schedule # Doses	N	None		Mild/Grade 1		Moderate/Grade 2		Severe/Grade 3		Missing	
				n	%	n	%	n	%	n	%	n	%
Baseline (Day 1)	ANDV DNA 2mg	3 or 4	x	x	xx	x	xx	x	xx	x	xx	x	xx
	ANDV DNA 4mg	3 or 4											
	Placebo	-											
	All Subjects	-											
Day 8 (Day 8 Post Dose 1)	ANDV DNA 2mg	3 or 4											
	ANDV DNA 4mg	3 or 4											
	Placebo	-											
	All Subjects	-											
Day 36 (Day 8 Post Dose 2)	ANDV DNA 2mg	3 or 4											
	ANDV DNA 4mg	3 or 4											
	Placebo	-											
	All Subjects	-											
Day 64 (Day 8 Post Dose 3)	ANDV DNA 2mg	3											
		4											
	ANDV DNA 4mg	3											
		4											
	Placebo	-											
	All Subjects	-											
Repeat for:													
Day 169 (Pre-Dose 4)													
Day 176 (Day 8 Post Dose 4)													
Max Severity Post Baseline													

Note: The “Max Post Baseline” rows indicate the maximum severity experienced by each subject at any time point post baseline, including unscheduled assessments.

N=Number of subjects in the Safety Population; n=Number of subjects with laboratory values in the respective category.

Tables with similar format:

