For baseline laboratory results that are abnormal according to the local laboratory reference range and fall within Grade 1 toxicity table range, these will not be considered laboratory adverse event (AE) and will thus not be graded. However, if baseline clinical labs fall within Grade 1 range, then a laboratory AE is reported only if the value changes such that it falls into Grade 2 or higher when subsequent safety laboratory testing is done.

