11.4.2 Safety Data

Summaries and analysis of safety data will be presented for the Safety Analysis Population.

Solicited AEs will be summarized by severity for each day after vaccination (Days 1-7 post study vaccination) and as the maximum severity over all 7 days. Additionally, solicited AEs will be analyzed by taking the most severe response over the follow-up period, dichotomizing into a binary variable (none versus mild, moderate, or severe) and using standard techniques, such as exact confidence intervals (CI), to summarize the proportion of subjects reporting each symptom, any application site symptom, and any systemic symptom.

Unsolicited non-serious AEs will be collected from the time of first study vaccination through approximately 28 days post last vaccination. Unsolicited AEs will be coded by Medical Dictionary for Regulatory Activities (MedDRA®) for preferred term and system organ class (SOC). SAEs will be collected from the time of first study vaccination through approximately 6 months post last vaccination. The numbers of SAEs are likely to be small in this trial and will be reported by detailed listings showing the event description, MedDRA® preferred term and SOC, relevant dates (study vaccinations and AEs), severity, relatedness, and outcome for each event.

Non-serious unsolicited AEs will be summarized as number and percentage of subjects reporting at least one event in each MedDRA® preferred term and SOC, cross tabulated by severity and relationship to study product. Additionally, the proportion of subjects and exact 95% confidence intervals of AEs in aggregate and by MedDRA® categories will be computed.

Clinical laboratory data will be summarized by severity for each visit, and as the maximum over all post-study vaccination visits. Graphical presentations may include box plots and shift plots.

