### **3.2. Endpoints**

#### **3.2.1. Primary Outcome Measures**

- Occurrence of vaccine-related Serious Adverse Events (SAEs) through approximately 6 months post last vaccination.
- Occurrence of vaccine-related unsolicited Adverse Events (AEs) through 28 days post last vaccination.
- Occurrence of Serious Adverse Events (SAEs) through approximately 6 months post last vaccination.
- Occurrence of unsolicited Adverse Events (AEs) through 28 days post last vaccination.
- Occurrence of solicited local and systemic AEs through 7 days after each study vaccination.
- Occurrence of clinical safety laboratory AEs through 7 days after each study vaccination.

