## 9.3. Adverse Events

When calculating the incidence of adverse events (i.e., on a per subject basis), each subject will only be counted once and any repetitions of adverse events within a subject will be ignored; the denominator will be the number of subjects in the Safety population. All adverse events reported will be included in the summaries and analyses.

An overall summary of adverse events is presented in [Table 47](#).

Adverse events occurring in 5% of subjects in any vaccination group will be presented in [Table 48](#).

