#### **9.6. Clinical Laboratory Evaluations**

Clinical safety laboratory adverse events are collected at the time of study vaccination through approximately 7 days after each study vaccination. Parameters evaluated include white blood cell count, platelet count, hemoglobin concentration, ANC, sodium, potassium, total bilirubin, alanine aminotransferase (ALT), and creatinine. If creatine is above the normal range, blood urea nitrogen (BUN) is also assessed. Grading scales for safety laboratory parameters are presented in [Table 10](#) and [Table 11](#).

A listing of subject visits with any abnormal chemistry laboratory results (Grade 1 severity or higher) will be presented in [Table 106](#). Subject visits with abnormal hematology laboratory results will be presented in [Table 107](#).

The distribution of abnormal chemistry laboratory results by maximum severity, time point, and vaccination group will be presented in [Table 108](#), [Table 109](#), [Table 110](#), [Table 111](#), [Table 112](#), [Table 113](#) and [Table 114](#).

The distribution of chemistry laboratory results assessed as related to study IP, by maximum severity, time point, and vaccination group will be presented in [Table 115](#), [Table 116](#), [Table 117](#), [Table 118](#), [Table 119](#), [Table 120](#), and [Table 121](#).

Descriptive statistics including mean, median, standard deviation, maximum and minimum values, by time point and vaccination group, for each chemistry laboratory parameter, including change from baseline, will be summarized in [Table 122](#), [Table 123](#), [Table 124](#), [Table 125](#), [Table 126](#), and [Table 127](#).

The distribution of abnormal hematology laboratory results by maximum severity, time point, and vaccination group will be presented in [Table 128](#), [Table 129](#), [Table 130](#), [Table 131](#), and [Table 132](#).

The distribution of hematology laboratory results assessed as related to study IP, by maximum severity, time point, and vaccination group will be presented in [Table 133](#), [Table 134](#), [Table 135](#), [Table 136](#), and [Table 137](#).

Descriptive statistics including mean, median, standard deviation, maximum and minimum values, by time point and vaccination group, for each hematology laboratory parameter, including change from baseline, will be summarized in [Table 138](#), [Table 139](#), [Table 140](#), and [Table 141](#).

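### SAP 9.6 does not apply the protocol's rule for Grade 1 baselines, and no planned table is identified as the count of laboratory AEs, a primary outcome

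*SAP*

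**What the plan says.** SAP 3.2.1 lists as a primary outcome "Occurrence of clinical safety laboratory AEs through 7 days after each study vaccination"; Protocol 3.2.1 has the same outcome.

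Protocol 9.2.4 defines what counts. For baseline results in the Grade 1 range, "these will not be considered laboratory adverse event (AE) and will thus not be graded". After such a baseline, "a laboratory AE is reported only if the value changes such that it falls into Grade 2 or higher". Baseline is the Day 1 value (note to SAP Tables 10 and 11).

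SAP 9.6 neither states nor cites this rule, and SAP section 14 does not list its omission as a change from the protocol. The section plans that "The distribution of abnormal chemistry laboratory results by maximum severity, time point, and vaccination group will be presented in" Tables 108-114, with the matching hematology displays in Tables 128-132. In the Table 108 shell, "n=Number of subjects with laboratory values in the respective category". The shell also grades the Day 1 row itself. Its final row is "the maximum severity experienced by each subject at any time point post baseline, including unscheduled assessments".

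These displays have a basis in the protocol. Protocol 11.4.2 says: "Clinical laboratory data will be summarized by severity for each visit, and as the maximum over all post-study vaccination visits". It does not mention the baseline rule either.

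**The concern.** A subject whose WBC is 4.0 K/mcL on Day 1 and at every later visit has had no laboratory AE under Protocol 9.2.4. Table 129 would still count that subject as Grade 1 at each post-vaccination visit and in the maximum row. The same holds in Table 111 for a woman with an unchanged creatinine of 0.9 mg/dL.

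The raw-grade tables are the only planned group summary of laboratory abnormalities regardless of relatedness, and their grades come from scales that the SAP titles as laboratory adverse event grading. A reader looking for the primary laboratory outcome is likely to take its incidence from them. The trial's stated purpose is preliminary estimation of safety (Protocol 11.1), so an absolute incidence that includes pre-existing Grade 1 values matters, even though no hypothesis is tested.

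**Working it through.** **1. The plan's own figures.** The documents give no expected laboratory-AE rate and no precision for this outcome, so there is nothing to reproduce for it directly. SAP Table 3 gives the chance of at least one event as 1 − (1 − p)^n. For p = 5%, 1 − 0.95^10 = 40.1% and 1 − 0.95^20 = 64.2%, which match the table. The same formula is used in step 6.

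**2. Can a subject enter with a Grade 1 baseline?** Yes. Comparing Protocol Appendix B with Protocol Tables 8 and 9:

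| Parameter | Accepted at entry | Grade 1 band | Overlap |
|---|---|---|---|
| WBC, low (K/mcL) | from 3.6 | 2.5-4.4 | 3.6-4.4 |
| Creatinine, women (mg/dL) | up to 1.2 | 0.81-1.70 | 0.81-1.2 |
| Creatinine, men (mg/dL) | up to 1.3 | 1.11-1.70 | 1.11-1.3 |

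The creatinine overlap applies when BUN is not raised (Protocol 8.2.2). The Day 1 safety labs that define baseline are not used to screen before dosing (Protocol 8.2.1), so other parameters can also be Grade 1 on Day 1.

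**3. The two counting rules, one parameter.** Take baseline grade 0 or 1 and maximum later grade 0 to 3, which gives 8 pairs. With baseline 0, the raw grade and the protocol grade agree in all 4 pairs. With baseline 1 they agree for later maxima of 0, 2 and 3. They differ only for baseline 1 with later maximum 1: Grade 1 in the raw table, no AE under the protocol. So 1 of 8 pairs changes, in one direction, within Grade 1.

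**4. Is the count elsewhere?**
- Table 47 has no laboratory row.
- Table 48 covers solicited and unsolicited AEs.
- Tables 115-121 and 133-137 hold only results judged related.
- SAP 9.3 says "All adverse events reported will be included in the summaries and analyses", but neither document says laboratory AEs are entered as unsolicited AEs. Protocol 9.1 and SAP 4.4.1 list them as a separate class. Even if they were entered so, the by-dose unsolicited tables run to the next dose, or to 28 days if it is not given (Table 81 note), not to 7 days.

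**5. Effect of one subject.** Group sizes from Protocol Table 1: 10 per vaccination group (1 sentinel plus 9), 20 per dose level, 8 on placebo (4 × 2), 48 in all. One persisting Grade 1 baseline with no new abnormality adds 1/20 = 5.0 points, 1/10 = 10.0 points or 1/8 = 12.5 points. As an illustration in a group of 10, two persisting Grade 1 baselines plus one new Grade 1 give 3/10 (exact 95% CI 6.7% to 65.2%) in the raw table. Under the protocol rule the result is 1/10 (0.3% to 44.5%).

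**6. Range under assumptions.** Let p be the share with a Grade 1 baseline and s the share of those whose maximum stays at Grade 1. Neither is in the documents. The excess in the raw Grade 1 percentage is p × s. With p from 2% to 20% and s from 0.5 to 1, it runs from 0.02 × 0.5 = 1 point to 0.20 × 1 = 20 points. The chance of at least one such subject is 1 − (1 − p·s)^n:

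| p | n = 20, s = 1 | n = 10, s = 1 | n = 8, s = 1 | n = 10, s = 0.5 |
|---|---|---|---|---|
| 2% | 33.2% | 18.3% | 14.9% | 9.6% |
| 5% | 64.2% | 40.1% | 33.7% | 22.4% |
| 10% | 87.8% | 65.1% | 57.0% | 40.1% |
| 20% | 98.8% | 89.3% | 83.2% | 65.1% |

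The s = 1 columns assume that every Grade 1 baseline persists, so they are upper bounds for each p.

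**7. Which draws belong to the outcome?** Days 8, 36, 64 and 176 are each 7 days after a vaccination (8 − 1, 36 − 29, 64 − 57, 176 − 169). Day 169 is pre-dose, 169 − 57 = 112 days after the third vaccination. The outcome is worded as 7 days after each vaccination, yet Protocol 9.3 reports laboratory AEs at Day 169 as well, and at re-evaluations of abnormal values through 7 days after the last vaccination. The documents do not settle which draws count.

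**The case against.** The strongest reply is that Tables 108-114 and 128-132 are titled abnormal results, not AEs, and do what Protocol 11.4.2 asks. They show the Day 1 grade distribution by group. Tables 122-127 and 138-141 give change from baseline. Tables 106-107 list each abnormal result by subject, and Listings 12-13 give all values. With 48 subjects the protocol count could be recovered. The effect can arise in every arm, and no hypothesis is tested.

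Most of this stands: the tables are legitimate and should stay. What remains is that a primary outcome has no planned count and no interval, and a reader would have to build it subject by subject. The Day 1 row gives group totals only, so it cannot supply the link.

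A reader might also infer more than the documents support:
- That unscheduled draws as such make the maximum row too wide. Protocol 7.8 and 7.9 collect safety labs at early-termination and unscheduled visits within 7 days of the last vaccination, so such draws can lie inside the outcome window.
- That the raw Grade 1 count can never fall below the AE count in any table. This holds for one parameter with a Grade 0 or 1 baseline. Protocol 9.2.4 has no rule for baselines of Grade 2 or higher. If a persisting Grade 2 baseline is not an AE, a subject with that plus a new Grade 1 in another parameter shows as Grade 2 in an any-parameter table but has a Grade 1 AE.
- That safety decisions are distorted. The laboratory halting rules need Grade 2 or higher in both sentinels, or Grade 3 in two or more subjects (Protocol 9.5), and the laboratory criterion for withholding later doses concerns Grade 3 (Protocol 5.4.3). None turns on the Grade 1 count.

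**Conclusion.** The point holds as a missing derivation and a missing table. SAP 9.6 does not carry Protocol 9.2.4 into the analysis, and no planned table is identified as the number of subjects with a protocol-defined laboratory AE. If the raw-grade tables are read as that number, Grade 1 incidence for a given parameter is equal to or above the protocol's figure for subjects with a Grade 0 or 1 baseline. In the any-parameter tables the excess can be smaller, because a subject with a new Grade 1 in another parameter is counted either way.

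That Grade 1 baselines are possible follows from the eligibility limits; how common they are is not stated. The per-subject effects rest only on the planned group sizes. The probabilities rest on an assumed p and are not forecasts. The consequence is for reporting the primary safety outcome, not for trial conduct.

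**What to change.** - In SAP 9.6, derive a laboratory-AE flag per subject and parameter from Protocol 9.2.4: Grade 1 or higher if Day 1 was normal, Grade 2 or higher if Day 1 was Grade 1. Ask the protocol team to clarify baselines of Grade 2 or higher, and changes in the opposite direction (for example, low on Day 1 and high later).
- Add one table of subjects with at least one laboratory AE, by parameter and vaccination group, with exact 95% CIs, and add a laboratory-AE row to Table 47.
- Include every scheduled or unscheduled draw inside the 7-day outcome window, allowing for the +2-day window on the Day 8 visits. A table limited to Days 8, 36, 64 and 176 could miss a true event found at an unscheduled draw.
- Reconcile the outcome window in Protocol 3.2.1 and SAP 3.2.1 with Protocol 9.3, and state whether Day 169 and re-evaluation draws count.
- Keep Tables 108-114 and 128-132 as the descriptive displays that Protocol 11.4.2 requires.

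The cost is a little programming, one table, one row and one protocol clarification. All inputs are already collected. The report will need a note explaining why laboratory-AE counts differ from the raw-grade counts.

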**Table 109: Abnormal Laboratory Results by Maximum Severity, Time Point, and Vaccination Group – Alanine Aminotransferase**

**Table 110: Abnormal Laboratory Results by Maximum Severity, Time Point, and Vaccination Group – Total Bilirubin**

**Table 111: Abnormal Laboratory Results by Maximum Severity, Time Point, and Vaccination Group – Creatinine**

**Table 112: Abnormal Laboratory Results by Maximum Severity, Time Point, and Vaccination Group – Sodium**

Time Point	Vaccination Group	ANDV DNA Schedule # Doses	N	None		Mild/ Grade 1 (Low)		Mild/ Grade 1 (High)		Moderate/ Grade 2 (Low)		Moderate/ Grade 2 (High)		Severe/ Grade 3 (Low)		Severe/ Grade 3 (High)		Missing	
				n	%	n	%	n	%	n	%	n	%	n	%	n	%	n	%
Baseline (Day 1)	ANDV DNA 2mg	3 or 4	x	x	xx	x	xx	x	xx	x	xx	x	xx	x	xx	x	xx	x	xx
	ANDV DNA 4mg	3 or 4																	
	Placebo	4																	
	All Subjects	3 or 4																	
Day 8 (Day 8 Post Dose 1)	ANDV DNA 2mg	3 or 4																	
	ANDV DNA 4mg	3 or 4																	
	Placebo	4																	
	All Subjects	3 or 4																	
Day 36 (Day 8 Post Dose 2)	ANDV DNA 2mg	3 or 4																	
	ANDV DNA 4mg	3 or 4																	
	Placebo	4																	
	All Subjects	3 or 4																	
Day 64 (Day 8 Post Dose 3)	ANDV DNA 2mg	3																	
		4																	
	ANDV DNA 4mg	3																	
		4																	
	Placebo	4																	
	All Subjects	3 or 4																	
Repeat for:																			
Day 169 (Pre-Dose 4)																			
Day 176 (Day 8 Post Dose 4)																			
Max Severity Post Baseline																			

Note: The “Max Post Baseline” rows indicate the maximum severity experienced by each subject at any time point post baseline, including unscheduled assessments.

N=Number of subjects in the Safety Population; n=Number of subjects with laboratory values in the respective category.

---

Table with similar format:

**Table 113: Abnormal Laboratory Results by Maximum Severity, Time Point, and Vaccination Group – Potassium**

Table with similar format to Table 108:

**Table 114: Abnormal Laboratory Results by Maximum Severity, Time Point, and Vaccination Group – Blood Urea Nitrogen**

**Table 115: Abnormal Laboratory Results Related to Study Treatment by Maximum Severity, Time Point, and Vaccination Group – Any Chemistry Parameter**

Time Point	Vaccination Group	ANDV DNA Schedule # Doses	N	Mild/ Grade 1		Moderate/ Grade 2		Severe/ Grade 3	
				n	%	n	%	n	%
Baseline (Day 1)	ANDV DNA 2mg	3 or 4	x	x	xx	x	xx	x	xx
	ANDV DNA 4mg	3 or 4							
	Placebo	4							
	All Subjects	3 or 4							
Day 8 (Day 8 Post Dose 1)	ANDV DNA 2mg	3 or 4							
	ANDV DNA 4mg	3 or 4							
	Placebo	4							
	All Subjects	3 or 4							
Day 36 (Day 8 Post Dose 2)	ANDV DNA 2mg	3 or 4							
	ANDV DNA 4mg	3 or 4							
	Placebo	4							
	All Subjects	3 or 4							
Day 64 (Day 8 Post Dose 3)	ANDV DNA 2mg	3							
		4							
	ANDV DNA 4mg	3							
		4							
	Placebo	4							
	All Subjects	3 or 4							
Repeat for:									
Day 169 (Pre-Dose 4)									
Day 176 (Day 8 Post Dose 4)									
Max Severity Post Baseline									

Note: The “Max Post Baseline” rows indicate the maximum severity experienced by each subject at any time point post baseline, including unscheduled assessments.

N=Number of subjects in the Safety Population; n=Number of subjects with laboratory values in the respective category.

Tables with similar format:

**Table 116: Abnormal Laboratory Results Related to Study Treatment by Maximum Severity, Time Point, and Vaccination Group – Alanine Aminotransferase****Table 117: Abnormal Laboratory Results Related to Study Treatment by Maximum Severity, Time Point, and Vaccination Group – Total Bilirubin****Table 118: Abnormal Laboratory Results Related to Study Treatment by Maximum Severity, Time Point, and Vaccination Group – Creatinine**

**Table 119: Abnormal Laboratory Results Related to Study Treatment by Maximum Severity, Time Point, and Vaccination Group – Sodium**

Time Point	Vaccination Group	ANDV DNA Schedule # Doses	N	Mild/ Grade 1 (Low)		Mild/ Grade 1 (High)		Moderate/ Grade 2 (Low)		Moderate/ Grade 2 (High)		Severe/ Grade 3 (Low)		Severe/ Grade 3 (High)	
				n	%	n	%	n	%	n	%	n	%	n	%
Baseline (Day 1)	ANDV DNA 2mg	3 or 4	x	x	xx	x	xx	x	xx	x	xx	x	xx	x	xx
	ANDV DNA 4mg	3 or 4													
	Placebo	4													
	All Subjects	3 or 4													
Day 8 (Day 8 Post Dose 1)	ANDV DNA 2mg	3 or 4													
	ANDV DNA 4mg	3 or 4													
	Placebo	4													
	All Subjects	3 or 4													
Day 36 (Day 8 Post Dose 2)	ANDV DNA 2mg	3 or 4													
	ANDV DNA 4mg	3 or 4													
	Placebo	4													
	All Subjects	3 or 4													
Day 64 (Day 8 Post Dose 3)	ANDV DNA 2mg	3													
		4													
	ANDV DNA 4mg	3													
		4													
	Placebo	4													
	All Subjects	3 or 4													
Repeat for:															
Day 169 (Pre-Dose 4)															
Day 176 (Day 8 Post Dose 4)															
Max Severity Post Baseline															

Note: The “Max Post Baseline” rows indicate the maximum severity experienced by each subject at any time point post baseline, including unscheduled assessments.

N=Number of subjects in the Safety Population; n=Number of subjects with laboratory values in the respective category.

Table with similar format to Table 119:

**Table 120: Abnormal Laboratory Results Related to Study Treatment by Maximum Severity, Time Point, and Vaccination Group – Potassium**

Table with similar format to Table 115:

**Table 121: Abnormal Laboratory Results Related to Study Treatment by Maximum Severity, Time Point, and Vaccination Group – Blood Urea Nitrogen**

